#### **6.6.5.2. ECG Parameter Results**

The absolute corrected QT interval (QTcB, QTcF, and/or QTcS) will be summarized using descriptive statistics (n, mean, median, standard deviation (SD), minimum, maximum and a 90% confidence interval for the mean) by cycle and nominal time point within cycle (Screening, Cycle 1: Day 1 at 0, 1, 2, 4 hours; Day 4 at 0, 2 hours; Day 7 at 0, 2, 4, 6, and Cycle 2 Day 1 at 0, 2 hours; Day 7 at 0, 2, 6. The 90% CI for the mean will be calculated using the t-distribution and the observed standard deviation from the particular timepoint.

In addition to QTc, the ECG parameters of HR, PR interval, QRS interval, QT interval will be summarized similarly with descriptive statistics (n, mean, median, standard deviation (SD), minimum, maximum).

#### **6.6.5.3. Change from baseline**

The change in QTc (QTcF, QTcB and/or QTcS) from baseline will be summarized using descriptive statistics (n, mean, median, standard deviation (SD), minimum, maximum for each cycle and nominal time point within cycle.

A linear model (for adult patients and pediatric patients separately) with the Cycle 1 nominal timepoints as a fixed effect and unstructured variance/covariance to account for the repeated measurements from patients will be used to estimate the mean change from baseline (in QTcB and/or QTcS) at the post baseline nominal timepoints for Cycle 1 along with the estimated least squares means and 2-sided 90% confidence interval for the mean.

Confidence intervals will use the approximate t distribution with degrees of freedom by Kenward Rogers method.

In addition to QTc, the change from baseline in ECG parameters of HR, PR interval, QRS interval, QT interval will be summarized similarly with descriptive statistics (n, mean, median, standard deviation (SD), minimum, maximum).

#### **6.6.5.4. Absolute QTc interval prolongation**

Categorical analysis of absolute QTc interval prolongation for QTc (QTcF and/or QTcS) according the maximum post-baseline value per patient will be summarized. . As described in Section 5.2.8.4, the categories of  $\leq 450$ ;  $>450 - \leq 480$ ,  $>480 - \leq 500$ ;  $>500$  msec will be used to classify post baseline values and the number and percentage of patients in each category will be summarized. A similar categorical analysis of HR, PR and QRS will be provided (HR  $\leq 50$  bpm, HR  $\geq 120$  bpm, PR  $\geq 220$  msec and QRS  $\geq 120$  msec).

Additionally a shift summary will be presented using CTCAE grade, where the baseline value will also be classified into the same categories and cross classified with the post baseline values. Baseline is based on the triplicate average, but worst post baseline interval measurements will be based on individual replicates including values from unscheduled ECGs. The baseline versus the worst on treatment QTc will be summarized.

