### 2.2. Study Design

This is a single-arm, open-label, Phase 4 study evaluating the effect of gemtuzumab ozogamicin (GO) on the QTc, pharmacokinetics, safety, and immunogenicity of GO as a single-agent monotherapy in adult and pediatric patients with relapsed or refractory CD33-positive AML. Approximately 50 adult (age  $\geq 18$  years) patients and 6 pediatric ( $12 \leq \text{age} \leq 17$  years) patients will be enrolled.

**Treatment Plan:** Three doses of GO 3 mg/m^2 (up to one vial) as a 2-hour intravenous infusion on Days 1, 4, and 7 at each cycle, up to 2 cycles. A second cycle of GO will be allowed at the investigator's discretion for patients who meet the following criteria after Cycle 1: Bone marrow with a decrease of blast percentage to at least 25% or a decrease of pretreatment blast percentage by at least 50%; **and** blood count with neutrophils  $\geq 1,000/\mu\text{L}$

and platelets  $\geq 50,000/\mu\text{L}$ , except in patients where the bone marrow blasts  $\geq 5\%$  and the decrease in neutrophils and platelets is thought to be due to the underlying leukemia.

After GO treatment, subsequent anticancer therapy such as consolidation or conditioning regimen and/or HSCT could be considered at the investigator's discretion. A minimum interval of 2 months is recommended between the last dose of GO and HSCT.

**Summary of Assessments:** Triplicate ECGs will be performed at screening, baseline (prior to dose on Day 1) and immediately preceding serial PK draws. All triplicate ECG tracings will be sent to an independent ECG core laboratory for blinded manual interval measurements.

Blood samples will be collected from all participating patients for PK analysis according to the PK schedule. Samples will be collected prior to each dose and at time points around the maximum concentration ( $C_{\max}$ ), i.e. at the end of the 2-hour infusion, in order to characterize the QTc-concentration relationship.

Anti-drug antibody (ADA) samples will be collected as specified in the protocol. Samples will be analyzed for ADAs using a tiered approach of screening, confirmation, and titer determination. Samples that test positive for ADA will be further characterized to determine whether neutralizing antibodies (NAb) are present.

CC1

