#### **5.2.8.4. Categorization of ECG parameters**

The categorization of QTc will be per ICH E14 guidance:

The absolute QTc interval (QTcF and QTcS) value for each patient will be categorized as  $\leq 450$ ;  $> 450 - \leq 480$ ,  $> 480 - \leq 500$ ;  $> 500$  msec, using the maximum value post baseline (considering both cycles) based on the averaged triplicate values. Similarly, the absolute values of HR, PR and QRS will be categorized as follows: HR  $\leq 50$  bpm, HR  $\geq 120$  bpm, PR  $\geq 220$  msec and QRS  $\geq 120$  msec.

The maximum increase from baseline QTc will be categorized as:  $\leq 30$  msec,  $> 30 - \leq 60$  msec and  $> 60$  msec based on the averaged triplicate values. Similarly, the maximum increase from baseline for HR will be categorized as  $\geq 20$  bpm and maximum increase from baseline for PR will be categorized as  $\geq 20$  msec.

CCI

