#### **6.6.5.5. Maximum increase from baseline QTc**

Categorical analysis of maximum increase from baseline in QTc (QTcF and/or QTcS) and will be summarized. . As described in Section 5.2.8.4, the categories of  $\leq 30$  msec,  $>30 - \leq 60$  msec and  $>60$  msec will be used and the number and percentage of patients in each category will be summarized. A similar categorical analysis of HR and PR will be provided (HR increase from baseline  $\geq 20$  bpm and PR increase from baseline  $\geq 20$  msec).

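### The HR, PR and QRS outlier counts ignore the baseline value, so with no control arm they mix pre-existing abnormality with new onset; only QTc gets a baseline shift table

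*SAP*

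**What the plan says.** SAP 5.2.8.4 first sets the absolute QTc categories for each patient, "using the maximum value post baseline (considering both cycles) based on the averaged triplicate values". It then continues: "Similarly, the absolute values of HR, PR and QRS will be categorized as follows", and lists HR ≤50 bpm, HR ≥120 bpm, PR ≥220 msec and QRS ≥120 msec. SAP 6.6.5.4 repeats these limits for the analysis: "A similar categorical analysis of HR, PR and QRS will be provided". Neither section refers to the baseline value of HR, PR or QRS.

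SAP 6.6.5.4 then adds a cross-classification: "Additionally a shift summary will be presented using CTCAE grade, where the baseline value will also be classified into the same categories". It closes with "The baseline versus the worst on treatment QTc will be summarized". Protocol 9.3.1 also describes the shift table for QTc only.

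Baseline enters the HR, PR and QRS reporting elsewhere:
- SAP 6.6.5.5: "A similar categorical analysis of HR and PR will be provided", with limits of a 20 bpm and a 20 msec increase. QRS is not included.
- SAP 6.6.5.3: change from baseline in HR, PR, QRS and QT, with n, mean, median, SD, minimum and maximum.
- SAP 6.6.5.2: absolute values of the same parameters, summarised in the same way as QTc, whose timepoints include Screening and Cycle 1 Day 1 hour 0.

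**The concern.** SAP 2.2 describes the design: "This is a single-arm, open-label, Phase 4 study evaluating the effect of gemtuzumab ozogamicin (GO) on the QTc". With one arm, each patient's own baseline is the only reference for a categorical ECG finding. A count of patients beyond a limit after dosing, taken without that reference, adds those who were there before GO to those who crossed the limit afterwards.

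Such patients can be enrolled. The only numeric ECG limit in protocol 4.2 is QTcF above 470 msec. Rhythm disorders are excluded when uncontrolled. A stable bundle branch block, first-degree AV block or fast resting rate is not excluded by a stated limit. Protocol 1.2.1 puts the average age of a patient with AML at about 68 years, so some conduction delay at entry is plausible.

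At stake is how these rows are read in a post-marketing ECG study. A non-zero QRS row could be taken as a GO finding when it is partly or wholly background, and a small true onset could be lost in the same total.

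**Working it through.** **1. The plan's own figure.** SAP 5.1 states 90% power with 50 adults, SD 18.8 msec, true change 10 msec, margin 20 msec and one-sided 0.05. The noncentral t gives 0.9805 at one timepoint, and 0.9805^5 = 0.906 for five independent timepoints. The stated power reproduces, and nothing below changes it.

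**2. Baseline reference for each categorical result.**

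| Parameter | Absolute limit | Baseline-by-worst table | Increase category |
|---|---|---|---|
| QTc | yes | yes | yes |
| HR | yes (≤50, ≥120) | no | ≥20 bpm |
| PR | yes (≥220) | no | ≥20 msec |
| QRS | yes (≥120) | no | none |

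The HR and PR increase counts are separate totals. They do not show which patients in the HR ≥120 or PR ≥220 row were already there before GO.

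**3. Patients carried over with no GO effect.** Let p0 be the proportion meeting a limit at baseline. The documents give no value, so 2% to 20% is an assumption, as is persistence of the abnormality after dosing. Expected carry-over is 50 × p0, and the chance of at least one carried-over patient is 1 − (1 − p0)^50.

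| p0 | Expected of 50 | Chance of at least one | Expected new-onset denominator, 50 × (1 − p0) |
|---|---|---|---|
| 2% | 1 | 64% | 49 |
| 5% | 2.5 | 92% | 47.5 |
| 10% | 5 | 99.5% | 45 |
| 20% | 10 | >99.9% | 40 |

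**4. Carry-over plus some new onset.** If a fraction i of the others cross the limit, the row shows p0 + (1 − p0) × i. With p0 = 10% and i = 2%, both assumed, this is 0.10 + 0.90 × 0.02 = 11.8%. Of that, 0.10 / 0.118 = 85% was present at baseline.

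**5. Random variation as well.** A simulation with no drug effect assumed QRS with mean 95 msec, between-patient SD 13, and within-patient SD 2 or 4 for a triplicate average. It took the maximum over the 9 Cycle 1 post-dose timepoints, or over 14 with Cycle 2 (SAP 5.2.8.3). The QRS ≥120 row then holds 2.3 to 4.2 of 50 patients. Of these, 1.4 to 1.6 were at or above the limit at baseline (38% to 61% of the row). The other 0.9 to 2.6 crossed by variation alone.

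**The case against.** The strongest reply is that baseline is not ignored in the ECG package. Change from baseline in QRS is summarised with its maximum, so a large individual increase would show. Absolute values are displayed at the baseline timepoints. HR and PR have increase counts. The cardiac conduction AESI (SAP 3.5.1.1, Appendix 2) counts events starting after first dose, so a stable pre-existing block should not appear there as new. All of this stands. A reader might infer that the study cannot show whether GO affects conduction or heart rate, or that a real QRS effect could not be separated from background. The documents do not support either inference: the gap is in the threshold counts.

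A second reply is that these counts carry no test or decision rule. The conclusion rests on adult QTcF at five timepoints. That also stands, and it limits the weight of the point.

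A third is that eligibility is not wide open. Recent infarction and heart failure are excluded, and criterion 18 lets the investigator exclude conditions that could cloud interpretation. This lowers the likely prevalence but sets no HR, PR or QRS limit.

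A fourth is that a baseline filter is an incomplete remedy. A change in QRS from 118 to 121 msec would still count as new, and step 5 shows that chance crossings remain. A count restricted to initially normal patients would also drop those already abnormal from view. This is fair, and it is why a full cross-tabulation is preferable to a filter alone.

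Finally, the words about the same categories in the shift sentence follow directly after the HR, PR and QRS list and could be read to include them. The closing sentence of SAP 6.6.5.4 and protocol 9.3.1 both name QTc only.

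**Conclusion.** The point holds for the absolute HR, PR and QRS counts in SAP 5.2.8.4 and 6.6.5.4. They combine pre-existing abnormality with new onset, and there is no control arm to separate the two. The gap is complete for QRS categories and partial for HR and PR.

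The size rests on an assumed baseline prevalence and on persistence of the abnormality: about 1 to 10 of 50 adults in a row at 2% to 20%. A reader might take the 85% in step 4 as an estimate, or infer that a false signal is likely. Neither is supported. The 85% depends on two chosen inputs, and under the assumptions of step 5 the pre-existing share of the QRS row is 38% to 61%.

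The primary QTcF analysis, the sample size and the power are unaffected. The change is still worth making, because it alters the reported counts at very little cost and matches the baseline-to-worst shift tables that SAP 6.6.3 already uses for laboratory data.

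**What to change.** In SAP 5.2.8.4 and 6.6.5.4, for each of HR ≤50, HR ≥120, PR ≥220 and QRS ≥120:

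- Cross-tabulate baseline status (triplicate average meeting or not meeting the limit) against worst post-baseline status.
- Report the new-onset count with patients not meeting the limit at baseline as the denominator.
- Show alongside it the number already meeting the limit at baseline, so that those patients stay visible.
- For HR ≤50, define worst as the minimum post-baseline value. If the maximum-value wording for QTc is carried over, a patient would count only when every post-baseline average was 50 bpm or lower.

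This also gives QRS a baseline-referenced categorical result. It will not remove chance crossings near a limit, so the table should be read beside the change-from-baseline summaries in SAP 6.6.5.3.

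The cost is minor programming and smaller denominators (an expected 49 to 40 of 50 over the assumed range). The baseline averages are already derived, and the QTc analysis set already requires a baseline ECG.

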#### **6.6.5.5. Maximum increase from baseline QTc**

Categorical analysis of maximum increase from baseline in QTc (QTcF and/or QTcS) and will be summarized. . As described in Section 5.2.8.4, the categories of  $\leq 30$  msec,  $>30 - \leq 60$  msec and  $>60$  msec will be used and the number and percentage of patients in each category will be summarized. A similar categorical analysis of HR and PR will be provided (HR increase from baseline  $\geq 20$  bpm and PR increase from baseline  $\geq 20$  msec).

#### **6.6.6. Physical Examination**

Physical examination data will be listed as needed to be compliant with ICH required listings and not summarized.

### **7. INTERIM ANALYSES**

Not applicable.

## 8. APPENDICES

### Appendix 1. SUMMARY OF PK ANALYSES

The following PK parameters will be calculated for GO (represented by total hP67.6 antibody, conjugated calicheamicin, and unconjugated calicheamicin) (if possible) from the concentration-time values using standard noncompartmental methods (Table 3).

**Appendix 1. Table 3. Noncompartmental PK Parameters**

Parameter	Analysis Scale	Total hP67.6 antibody	Conjugated calicheamicin	Unconjugated calicheamicin
AUC inf *	Ln	D	D	D
AUC last	Ln	D	D	D
AUC 0-72	Ln	D	D	D
AUC 0-336	Ln	D	D	D
C max	Ln	D	D	D
T max	R	D	D	D
t 1/2 *	R	D	D	D
CL*	Ln	D	D	D
V ss *	Ln	D	D	D

Key: D=displayed with descriptive statistics, ln=natural-log transformed, R=raw (untransformed), \*=if data permits.

## Appendix 2. AESI Definitions

**HEPATOTOXICITY: (Severe (Grade  $\geq 3$ ) and/or serious hepatotoxicity including all VOD/SOS) encoded to MedDRA preferred terms (PTs) within the following Standardised MedDRA Query SMQ and PTs:**

SMQs:

- Cholestasis and jaundice of hepatic origin (SMQ narrow)
- Hepatic failure, fibrosis and cirrhosis and other liver damage-related conditions (SMQ narrow)
- Hepatitis, noninfectious (SMQ narrow)
- Liver related investigations, signs and symptoms (SMQ narrow and broad)

PTs:

Hepatic vein occlusion  
Hepatic vein thrombosis  
Portal vein thrombosis  
Portal vein occlusion  
Budd-Chiari syndrome

All AES encoded to the following MedDRA PTs:

- Venoocclusive liver disease
- Venoocclusive disease

**HEAMORRHAGE:**

SMQ:

Haemorrhage terms (excluding laboratory terms) (SMQ narrow)

**MYELOSUPPRESSION:** AEs encoded to MedDRA preferred terms (PTs) within the following SMQ:

- Haematopoietic thrombocytopenia (SMQ narrow and broad)
- Haematopoietic leukopenia (SMQ narrow)
- Haematopoietic erythropenia (SMQ narrow and broad)
- Haematopoietic cytopenias affecting more than one type of blood cell (SMQ narrow)

**INFECTIONS: Grade  $\geq 3$  AEs and/or serious** AEs encoded to MedDRA preferred terms (PTs) within the following SOC and HLT

SOC (General infections):

- Infections and Infestations SOC

HLTs (Lung infections):

- Bacterial lower respiratory tract infections
- Fungal lower respiratory tract infections
- Lower respiratory tract infections NEC

- Respiratory tract infections NEC
- Viral lower respiratory tract infections

**INFUSION RELATED REACTIONS (including Anaphylaxis):** From start of infusion to within 24 hours of end of infusion:

Include events that occurred from start of infusion to within 24 hours of end of infusion:

SMQ:

- Anaphylactic reaction (SMQ narrow)
- Angioedema (SMQ narrow)
- Hypersensitivity (SMQ narrow)

PT:

- Cytokine release syndrome
- Infusion related reaction
- Chills
- Pyrexia
- Hot flush
- Flushing
- Feeling hot
- Hyperhidrosis
- Dizziness
- Dyspnoea
- Wheezing
- Tachycardia
- Hypotension

Thus only AEs that start within a window according to the treatment exposure records of the start of the GO infusion in terms of date and time to 24 hours after the date and time of the stop of the infusion. Since the AE CRF collects only AE start date and not start time, the AE start date will be compared to the date part only of the exposure window (rather than using imputed time of AE start).

## **TUMOUR LYSIS SYNDROME:**

SMQ:

Tumour lysis syndrome (SMQ narrow)

## **CARDIAC CONDUCTION:**

SMQ Cardiac arrhythmias; Torsade de pointes/QT prolongation (SMQ narrow and broad)
